#### **3.1.2. HANDLING OF DROPOUTS OR MISSING DATA**

All data will be used in the analyses. No imputation will be carried out for missing data.

## 4. ANALYSIS OF SAFETY

### 4.1. *Maintenance of Endothelial Cell Density*

#### 4.1.1. DESCRIPTION

Endothelial cell density will be collected [REDACTED] centrally [REDACTED]. Three images at the center of the cornea [REDACTED] are planned. Data reported on the CRF by the central reading center will include endothelial cell density and number of cells that were analyzed for each analyzable image. All recorded data from images will be used in the analysis. Although the central reading center will record the data separately for each image, the average cell density of the analyzable images for an individual eye for each corneal location (central [REDACTED]) will be used in all summary analyses.

#### 4.1.2. ENDOTHELIAL CELL LOSS OVER TIME (CHRONIC)

Chronic endothelial cell loss is defined as loss from the Day 147-182 (Form 5 or 5A) visit (in the previous studies) to any subsequent visit.

##### 4.1.2.1. CHRONIC CHANGE FROM DAY 147-182 (MONTH 6 IN PREVIOUS STUDIES)

[figure not shown]
Descriptive statistics will be provided for each scheduled visit, for [REDACTED] central [REDACTED] endothelial cell density, for all eyes combined. The statistics presented for endothelial cell density (using the average from the analyzable images for each eye) will include mean, median, standard deviation, sample size, minimum, and maximum.

[figure not shown]
The percent change of mean endothelial cell density over time from Day 147-182 (Form 5 or 5A) in the previous studies to each visit in the current study will be calculated. The actual and annualized percent change of mean endothelial cell density from the Day 147-182 (Form 5 or 5A) exam to each scheduled visit in this study will be calculated and presented along with median, standard deviation, sample size, minimum and maximum. Tables presenting the mean, median, standard deviation, sample size, minimum and maximum of baseline (Form 5 or 5A in previous studies) endothelial cell density and cell density change from baseline to each scheduled visit in this study will be presented for all eyes combined.

[figure not shown]
#### 4.1.2.2. POSTOPERATIVE CHANGE FROM PREOPERATIVE BASELINE

[figure not shown]
Descriptive statistics will be provided for change from preoperative baseline (in previous studies) to each scheduled visit in this study, for [REDACTED] central [REDACTED] endothelial cell density, for all eyes combined. The statistics presented will include mean, median, standard deviation, sample size, minimum and maximum. The percent change of mean endothelial cell density from preoperative baseline (Form 0 or 0A in previous study) to each scheduled postoperative visit (both in previous studies and this study) will be calculated to determine subjects who had  $\geq 30\%$  loss. A table showing the number and percent of eyes which had the onset of  $\geq 30\%$  endothelial cell loss (central [REDACTED]) from the preoperative level or central [REDACTED] of  $\leq 1500$  endothelial cells/mm^2 (occurring 6 months or later following implantation) will be presented.

[figure not shown]
In addition, the mean actual and annualized percent change of endothelial cell density (using the average from the analyzable images for each eye) of all subjects from baseline to each visit will be calculated and presented along with median, standard deviation, sample size, minimum and maximum. These tables will be presented for all eyes combined.

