#### **9.3.7. ENDOTHELIAL CELL DENSITY ANALYSIS**

Endothelial cell density [REDACTED] will be measured using the same methods as in the previous studies (C-02-23, C-02-40, C-03-21, C-05-57). The Konan Noncon-Robo specular microscope will be used to photograph corneal endothelial cells. Three images at the center of the cornea [REDACTED] shall be obtained.

Images shall be stored on the computer hard drive at the clinical site. Electronic copies of the images will be sent to a central reading center for analysis. For consistency, the central reading center ([REDACTED]) used for the previous studies, will be used for this study; Alcon personnel will not be involved in image analysis. The process for analyzing images at [REDACTED] will remain unaltered from that done in previous studies. Briefly, images received at [REDACTED] [REDACTED] will be reviewed by an initial reader and assessed for image quality. If image quality is acceptable then images will be analyzed. If images are deemed unanalyzable, then images will not be analyzed, and the site and Sponsor will be notified. (If there is a trend of unanalyzable images for a specific site/delegated study

personnel, retraining will be provided.) The subject will be asked to return and repeat the image capture and new images will be analyzed and used in the dataset. Analyzed images will be audited by a quality control reviewer [REDACTED]

Data reported by the central reading center will include endothelial cell density, [REDACTED]

[REDACTED] The site will receive a copy of the analysis to enter results in eCRFs.

The critical ECD threshold needed to sustain corneal endothelial cell function varies among individuals. Thus, it is critical to have regular examinations of the cornea every 6 months.

[figure not shown]
Criteria that may warrant more frequent examinations include:

- <1500 cells/mm^2 (central [REDACTED])
- >10% ECL in one year
- >30% ECL from preoperative baseline

[REDACTED]

When the central ECD approaches approximately 1500 cells/mm^2, the investigator should consider the potential need to undergo IOL explantation to reduce the risk of corneal decompensation and subsequent surgical interventions (such as corneal transplantation or DSEK). [REDACTED]

[REDACTED]

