#### **9.4. *Unscheduled Visits***

If a subject is examined more than once during any of the scheduled follow-up periods or if the subject is examined between scheduled follow-up periods, or if there is an unscheduled planned treatment delaying exit, an Unscheduled Visit Form must be completed.

If, during the visits for the 2nd eye implanted (Year 4A through 10A Forms), a clinically-relevant finding is noted for the 1st eye implanted, an unscheduled visit form must be completed to record the data for the 1st eye implanted; the same is true if a clinically-relevant finding is noted on the 2nd eye during the visits for the 1st eye. If the second eye examination is being conducted at the same time as a scheduled first eye examination (with both examinations occurring during the correct time frame) the findings from each eye should be recorded on the applicable visit form and not on an unscheduled visit form.

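### Loss of 30% or more is determined at scheduled visits only, so an eye whose only qualifying on-lens reading is unscheduled can go uncounted

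*SAP*

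**What the plan says.** **Determination of significant loss.** In SAP 4.1.2.2 the percent change from preoperative baseline "to each scheduled postoperative visit (both in previous studies and this study) will be calculated to determine subjects who had" at least 30% loss. The next sentence promises the output: "A table showing the number and percent of eyes which had the onset of" at least 30% loss, or a central density of 1500 cells/mm² or less, at 6 months or later. That second sentence names no visit type.

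**Where extra exams are recorded.** Under Protocol 9.4, when a subject is "examined more than once during any of the scheduled follow-up periods or if the subject is examined between scheduled follow-up periods", "an Unscheduled Visit Form must be completed".

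**Why extra exams arise.** Protocol 9.3.7 states: "Criteria that may warrant more frequent examinations include" a density below 1500 cells/mm², more than 10% loss in one year, and more than 30% loss from preoperative baseline. It also asks the investigator to consider explantation as central density nears about 1500.

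**What happens after explantation.** SAP 3.1.1 removes later density readings from all analyses except a post-explant loss analysis, unless another L-series lens was implanted.

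**Visit mapping.** Protocol 9.1 lets certain exams after Day 3740 count as Year 10/10A. No visible rule assigns other unscheduled density readings to a scheduled visit.

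**The concern.** Each rule is reasonable alone. Together they can discard a valid reading. An eye that is losing cells quickly may be examined between scheduled visits, be found at 30% loss or more with the lens still in place, and be explanted before its next scheduled visit. The qualifying reading is on an Unscheduled form, and the next scheduled reading is post-explant and excluded. Read literally, SAP 4.1.2.2 does not determine that eye as a case.

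The number and percent of eyes with significant loss is a main safety output of a study whose purpose is long-term endothelial safety. The flagged eyes are also the natural case set for the secondary objective on risk factors. Any eye lost this way would tend to be a fast loser, so the omission is not neutral.

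**Working it through.** The plan states no figure for this count, and Protocol 11 gives no power or precision calculation. The check is therefore on the rules, followed by arithmetic to see whether the sequence can occur.

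**1. Direction.** Let S be an eye's scheduled on-lens readings and U its unscheduled ones. The literal rule counts the eye if any reading in S shows at least 30% loss. The alternative counts it if any reading in S or U does. S is contained in S plus U, so the alternative count is equal or higher. With the same denominator, the scheduled-only share can only be equal or lower.

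**2. Is there time between scheduled visits?** The windows in Protocol Table 17.-1 include Day 1794–1915 (Year 5), 1976–2097 (Year 5.5) and 2159–2280 (Year 6).
- Longest interval between two on-time exams, Year 5 to 5.5: 2097 − 1794 = 303 days.
- Year 5.5 to 6: 2280 − 1976 = 304 days.
- Nominal spacing: 1976 − 1794 = 182 days and 2159 − 1976 = 183 days.

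Assume linear loss of r percentage points of the preoperative value per year. An eye below 30% at one scheduled exam crosses within d days if its loss there is at least 30 − r × d/365.25.

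| r (assumed) | d = 183 | d = 304 |
|---|---|---|
| 5 | 27.5% | 25.8% |
| 10 | 25.0% | 21.7% |
| 15 | 22.5% | 17.5% |

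So an eye can be unflagged at one scheduled visit and cross before the next.

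**3. One assumed eye.** Preoperative density is 2200 cells/mm². The last scheduled reading is 25% loss (2200 × 0.75 = 1650). An unscheduled reading shows 31% loss (2200 × 0.69 = 1518). At 10 points per year those 6 points take 6/10 × 365.25 = 219 days, which fits within 304. If the lens is then removed and not replaced by an L-series lens, the scheduled-only rule sees a maximum of 25% and does not count the eye. The all-readings rule sees 31% and counts it. The 1500 criterion does not rescue it, since 1518 is above 1500.

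**4. How narrow is the group?** The two thresholds coincide at a preoperative density of 1500/0.7 = 2143. Above that, an eye passes 30% loss before it reaches 1500. The points per year needed to go from just under 30% loss to 1500 within 304 days are 100 × (0.7P − 1500)/P × 365.25/304:
- P = 2500: 10.0 points, or 12.0 per year.
- P = 2800: 16.4 points, or 19.7 per year.
- P = 3200: 23.1 points, or 27.8 per year.

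At higher preoperative densities, omission through explantation near 1500 needs very fast loss. Explantation at a higher density, or for another reason, needs less.

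**5. Effect on the percentage.** The documents give no count of unscheduled exams, explants or cases. With assumed counts over the planned maximum of 1321 eyes:

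| Eyes flagged | 1 missed | 5 missed | 10 missed |
|---|---|---|---|
| 13 (0.98%) | 1.06% | 1.36% | 1.74% |
| 40 (3.03%) | 3.10% | 3.41% | 3.79% |
| 66 (5.00%) | 5.07% | 5.37% | 5.75% |

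**The case against.** The strongest reply is that the SAP does not expressly exclude unscheduled readings. SAP 3.1.2 says all data will be used, and SAP 4.1.1 says the same of recorded image data. SAP 4.1.2 defines chronic loss to any later visit, and the last paragraph of 4.1.2.2 speaks of each visit without qualification. The sentence describing the onset table, which contains the 1500 criterion, also omits *scheduled*. The SAP contents show a redacted heading between 4.1.2 and 4.2, and the post-explant loss analysis is not visible, so a governing rule may exist out of sight. This stands as a reason for caution about intent. It does not settle the matter: the one sentence that says how 30% loss is determined is tied to scheduled visits, and the general sentences do not say how an unscheduled reading enters that calculation.

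A second reply is that few eyes are exposed. This largely stands. Two of the three visible prompts for extra exams are themselves close to the counting thresholds, so eyes meeting them at a scheduled visit are generally counted already. The prompt for more than 10% loss in a year is the one that clearly reaches uncounted eyes, and extra exams are suggested, not mandated. An eye that keeps its lens and stays in follow-up is counted at its next scheduled visit if the loss persists, so its onset is late but not missed.

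Third, explanted eyes remain visible: through the Serious Adverse Event Form (Protocol 8.1.1), narratives and the post-explant analysis. That is true, but none of these puts the eye into the reported percentage.

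**Conclusion.** The point holds in a limited form. On the natural reading of SAP 4.1.2.2, an eye whose only on-lens reading at 30% loss or more is unscheduled can be left out if explantation without L-series replacement, exit or missed visits prevent a qualifying scheduled reading. The direction is certain relative to a count of all recorded on-lens readings: the share can only be understated. The size is unknown and may be small. The percentages tabulated above are illustrations from assumed counts, not estimates.

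Three stronger readings are tempting but unsupported:
- **Repeat imaging is lost.** Protocol 9.3.7 says otherwise: "The subject will be asked to return and repeat the image capture and new images will be analyzed and used in the dataset". It names no form, and nothing keeps those images out of the visit they replace.
- **Days between windows mean lost exams.** Visits are booked to windows, and Protocol 9.5 requires rescheduling within the same period. Protocol 9.1 refers to an early Year 10 exam, which suggests that a scheduled form can carry an out-of-window reading.
- **The 1500 criterion is equally restricted.** The word *scheduled* is attached to the 30% determination. For 1500 the visit basis is simply unstated.

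**What to change.** In SAP 4.1.2.2, state that onset of at least 30% loss, or of 1500 cells/mm² or less, is determined from every analyzable on-lens central reading at 6 months or later, scheduled or unscheduled, including the last reading before explantation. Report the count restricted to scheduled visits as a sensitivity result. The descriptive tables by scheduled visit in SAP 4.1.2.1 can stay as they are. If a redacted section already contains such a rule, a cross-reference is enough.

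The cost is a sentence or two in the SAP and a programming step that reads density from the Unscheduled forms. No new data are collected. The change should be made before database lock, when evaluability is finalized. The downside is that eyes examined more often have more chances to cross a threshold, including through measurement noise. Showing both counts lets the reader judge how much that matters.

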#### **8.1.1. IMPLANT REMOVALS**

During this clinical investigation, the implant may be removed at any time at the request of the study subject and/or if the investigator believes it appropriate (eg, cataract surgery). An implant removal is considered a Secondary Surgical Intervention and requires the completion of a Serious Adverse Event Form (see Section 12). Test article will not be provided for IOL replacement. Subjects with implant removals will not be exited from the study.

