## **3. DATA SETS ANALYZED**

### ***3.1. Safety***

#### **3.1.1. EVALUABILITY STRATEGY**

All subjects enrolled in the study will be considered evaluable for the safety analysis. All data collected in the study will be considered evaluable for the safety analysis with one exception. For subjects who have their AcrySof® CACHET® L-series Phakic Lens explanted and not replaced with another AcrySof® CACHET® L-series Phakic Lens, the post-explantation endothelial cell density data will be excluded from the statistical analyses other than a post-explant endothelial cell loss analysis. The post-explantation data will be used in subject narratives. The final evaluability (exclusion of post-explantation endothelial cell density data) will be determined prior to database lock.

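### The SAP 4.1.2.2 table counts marked cell loss on recorded density only, so an eye explanted for cell loss before meeting either criterion is left out of the count

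*SAP*

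**What the plan says.** - **The table.** SAP 4.1.2.2 describes "A table showing the number and percent of eyes which had the onset of" either of two density findings from six months after implantation: a fall of 30% or more from the preoperative level, or a value of 1500 cells/mm² or less. Both criteria carry a redaction directly after the word central. For the first, percent change is taken "to each scheduled postoperative visit (both in previous studies and this study) will be calculated to determine subjects who had" a loss of that size. No visit set is given for the second, and no denominator is given for the percent.
- **The prompt to consider removal.** Protocol 9.3.7: "When the central ECD approaches approximately 1500" cells/mm², "the investigator should consider the potential need to undergo IOL explantation to reduce the risk of corneal decompensation".
- **What happens to later readings.** SAP 3.1.1: if the lens is removed and no other L-series lens takes its place, "the post-explantation endothelial cell density data will be excluded from the statistical analyses other than a post-explant endothelial cell loss analysis". SAP 3.1.2: "No imputation will be carried out for missing data".
- **Who is evaluable.** SAP 3.1.1: "All subjects enrolled in the study will be considered evaluable for the safety analysis".
- **Where explants are reported.** Protocol 8.1.1: "An implant removal is considered a Secondary Surgical Intervention and requires the completion of a Serious Adverse Event Form".

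**The concern.** Removal is prompted by the same quantity that the table counts. Where a lens comes out because density is falling, the removal also ends that eye's chance of being counted, since later readings are set aside and nothing replaces them. An eye whose cell loss led to surgery can then sit in the same group as an eye with a stable endothelium.

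This is the readable table that counts eyes with marked loss, and the secondary objective (Protocol 5) looks for risk factors in eyes with substantial loss. Leaving out eyes explanted for cell loss would understate how often marked loss occurred. If the same classification were used to look for risk factors, those eyes would be put in the wrong group.

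**Working it through.** **Plan's own figure.** There is none to reproduce. The plan states no expected event rate, no explant count and no preoperative density distribution. Protocol 11 gives an upper limit of 1321 eyes, and Protocol 10.7 plans no tests.

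**The counting rule on central density.** Let P be the preoperative density and d the lowest eligible reading (six months or later) before explantation. The lowest reading matters because onset at any eligible visit counts.

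- Counted if d ≤ 1500 or d ≤ 0.70 × P.
- Not counted if d > 1500 and d > 0.70 × P, that is, if d > 1500 and P < d/0.70.

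| Lowest reading before explantation | Not counted if P is below |
|---|---|
| just above 1500 | 1500/0.70 = 2143 |
| 1550 | 1550/0.70 = 2214 |
| 1600 | 1600/0.70 = 2286 |
| 1700 | 1700/0.70 = 2429 |

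**Examples.**
- P = 2200, d = 1580: loss = (2200 − 1580)/2200 = 28.2%. The 30% line is 0.70 × 2200 = 1540. Neither criterion is met, and later readings do not enter this table.
- P = 2800, d = 1600: loss = (2800 − 1600)/2800 = 42.9%. The eye is already counted through the 30% criterion.

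**Direction.** With N eyes, x counted and k left out, the density-only percent is x/N if the k eyes stay in the denominator and x/(N − k) if they are removed from it. The combined percent is (x + k)/N. It is larger than x/N. It is also at least x/(N − k), because (x + k)(N − k) − xN = k(N − x − k) ≥ 0. So the omission cannot raise the percent.

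**Size.** Each eye moves the percent by 1/1321 = 0.076 points if all 1321 eyes are the denominator. How many eyes are affected can only be illustrated. A simulation of central density used these inputs, all assumed:

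- preoperative mean 2600 or 2800, SD 250 or 350, lowest value 1700, 2000 or 2200;
- 3% surgical loss, then chronic loss of 1.0 (SD 1.0), 1.5 (SD 1.5) or 2.5 (SD 2.0) % per year;
- measurement CV 2% or 5%;
- visits at Month 6, Years 1 to 5, then every six months to Year 10;
- explantation from Year 4 with probability 0.25, 0.5 or 0.9 per reading at or below 1550, 1600 or 1700;
- both criteria read at the same visits.

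This gives 2 × 2 × 3 × 3 × 2 × 3 × 3 = 648 sets.

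| Explanted eyes meeting neither criterion | Median | 10th–90th percentile |
|---|---|---|
| as share of explanted eyes | 23.5% | 3.8–68.6% |
| as share of counted eyes | 4.9% | 0.4–33.3% |

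- By reading at which explantation starts (1550, 1600, 1700), the median share of counted eyes is 1.2%, 3.7% and 17.3%.
- By lowest preoperative value (1700, 2000, 2200), it is 8.0%, 6.3% and 1.5%.

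If 5% of eyes were counted (an assumption), 1321 × 0.05 = 66. Then 66 × 0.049 = 3.2 eyes are left out, with a range of 66 × 0.004 = 0.3 to 66 × 0.333 = 22. The percent would move from 66/1321 = 5.0% to 69/1321 = 5.2%, or to 88/1321 = 6.7% at the upper end. In the 112 sets where 2–10% of eyes were counted, the share was 5.9% (0.4–44%), that is 66 × 0.059 = 3.9 eyes, with a range of 0.3 to 66 × 0.44 = 29.

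**Visit set.** The 30% criterion is tied to scheduled visits. The text does not say whether an unscheduled reading taken before explantation counts toward 1500. The effect is probably very small and was not computed.

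**The case against.** **Redaction.** Both criteria have a redaction after the word central, and SAP 4.1.1 averages density by corneal location. If another location is named, the 2200-to-1580 eye might be counted through it. SAP 3.1.1 names a post-explant loss analysis that no readable section describes, and the SAP contents list has a redacted entry starting at page 11, before 4.2 at page 15. This stands: the point holds only for the readable text.

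**The table is right on its own terms.** An eye at 1580 with 28% loss had neither finding, and the SAP does not promise a composite with explantation. This also stands, which is why the density-only count should stay. It does not remove the need to show beside it how many eyes had their follow-up for this count ended by explantation for cell loss.

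**Explants are not hidden.** They are SAEs and appear in narratives and in the post-explant analysis. The SAP 4.2.2 listing gives subject, eye, onset day, lens model and causality. That is true, but the tables are by Preferred Term and the listing fields named include neither last density nor percent loss. No readable text links explants to this table.

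**The size is assumed.** It is. About two-thirds of the simulated sets put more than 10% of eyes in the count, so the 5% base is a choice, and the ranges are too wide to serve as an estimate.

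**The reason for removal may not be on file.** Protocol 12.2 names no such field among the event details. Adverse events are collected here only from consent, while subjects already explanted may enrol (Protocol 7.2). This stands and shapes the fix.

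**Conclusion.** On the readable text, an eye explanted for cell loss without another L-series lens, and with every earlier eligible central reading above both 1500 and 0.70 of its preoperative value, is not counted in the SAP 4.1.2.2 table. If all evaluable eyes form the denominator, which the SAP does not state for this table, it appears as event-free. The omission can only lower the percent. The number of eyes cannot be computed from the documents and is probably small. It would be larger if removals happen well above 1500 or if many preoperative densities were below about 2300.

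The documents do not support four stronger readings:

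- A reader might infer that all eyes explanted near 1500 are missed. They are not: the 30% criterion already counts those with a higher preoperative density.
- A reader might infer that Protocol 9.3.7 has lenses removed above 1500. It asks only that the need be considered near an approximate value.
- A reader might infer that the plan has no explant analysis. Redacted text may contain one.
- A reader might carry the point over to the primary annualized rate. Nothing here bears on that rate.

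This is worth correcting in the SAP because the direction is known and the cost is low. It does not invalidate the analysis.

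**What to change.** In SAP 4.1.2.2, keep the density-only count and show beside it:

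1. eyes explanted with endothelial cell loss as the recorded reason and neither criterion recorded before explantation, with eyes of unknown reason on a separate line;
2. the combined count.

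Take the reason from SAE forms and narratives for explants in this study, and from the previous-study records for earlier ones. The sponsor should confirm that the reason can be obtained. State the denominator and one visit set for both criteria. If unscheduled readings are included, also give the scheduled-only count. If a redacted section already provides this, a cross-reference is enough.

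The cost is SAP wording, two table lines, some review of explant reasons, and a combined percent that may be higher than the density-only one. The change concerns counting only and leaves the explantation guidance as it is.

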### ***9.6. Discontinued Subjects***

Discontinued subjects will not be replaced. If a subject is discontinued from the study due to their death, the Exit Form and a Serious Adverse Event/Adverse Device Effect Form must be completed.

Subjects who require an IOL explant will not be discontinued and all reasonable efforts must be made to follow them up through their final study visit (Year 10/10A).

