### ***9.7. Subject Lost to Follow-Up***

A subject is considered lost to follow-up if:

- a) a postoperative Study Visit is overdue, all efforts to contact the subject for an examination have failed, the subject's last visit window has closed, or
- b) the subject is unable to make future office visits, or
- c) the subject has moved and is no longer able to be examined.

If a subject moves before completing all of the required visits, reasonable efforts must be made for the subject to return to the implanting investigator or to the closest investigational site for follow-up. Reimbursement for reasonable travel costs may be available from the Sponsor and will be addressed on a case-by-case basis.

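### The marked-loss table is one crude percent of eyes with no stated denominator, horizon or number at risk; if all enrolled eyes are counted, it understates the Year 10 share as retention worsens

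*SAP*

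**What the plan says.** SAP 4.1.2.2 plans "A table showing the number and percent of eyes which had the onset of" a loss of at least 30% from the preoperative level, or a central density of 1500 cells/mm² or fewer. It limits onset to that "occurring 6 months or later following implantation". Loss from the preoperative level is computed at scheduled postoperative visits in both the parent studies and this one. The readable text names no closing time, no denominator and no count of eyes at risk.

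Three other rules bear on the table:

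- SAP 3.1.1: "All subjects enrolled in the study will be considered evaluable for the safety analysis". The one exception is for lenses explanted and not replaced with the same series, where "the post-explantation endothelial cell density data will be excluded from the statistical analyses other than a post-explant endothelial cell loss analysis".
- SAP 3.1.2, the only dropout rule: "All data will be used in the analyses. No imputation will be carried out for missing data".
- Protocol 9.6 and 9.7 foresee follow-up that ends with the lens in place. "Discontinued subjects will not be replaced", and the list that opens "A subject is considered lost to follow-up if" includes subjects who cannot attend or have moved away.

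Protocol 8.1 intends follow-up to Year 10/10A.

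**The concern.** An onset at Year 8 can be recorded only in an eye still being read at Year 8. With every enrolled eye in the denominator, an eye that leaves at Year 5 without onset adds nothing to the numerator and a full unit to the denominator, exactly like an eye read free of the event at Year 10. The resulting percent mixes lengths of follow-up and refers to no particular time since implantation. It also moves the wrong way for a safety measure: worse retention gives a lower figure.

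The secondary objective concerns eyes with significant endothelial loss, and this table is the only count of such eyes in the readable SAP. The by-visit density summaries give means and sample sizes, not the share of eyes that cross a threshold.

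**Working it through.** The plan has no figure to reproduce. Protocol Section 11 sets the sample size by participation and states no event or attrition rate. What follows illustrates size on assumed inputs.

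**From the documents.** Up to 778 subjects and 1321 eyes (Protocol Section 11), so 1321 − 778 = 543 bilateral subjects if both maxima are reached. Visits are at Years 4, 5 and then half-yearly to Year 10 (Protocol Table 17.-1). The threshold is 30% loss from the preoperative level (SAP 4.1.2.2). The 1500 cells/mm² limb is not modelled.

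**Assumed.** Loss by Month 6 has mean 3%, SD 3%. Later loss is linear with mean 1.5% a year, SD 1.2%. All eyes are read to Year 4. After that, subjects leave non-informatively at yearly rate *a*. There is no reading noise and no explantation. Fellow-eye correlation is 0.6, which affects only the standard error.

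**Step 1: share with onset by year t.**
F(t) = 1 − Φ{[30 − 3 − 1.5(t − 0.5)] / √[3² + (1.2(t − 0.5))²]}
F(10) = 1 − Φ{(30 − 17.25)/√(9 + 129.96)} = 1 − Φ(1.08) = 14.0%.
Likewise F(7) = 2.0%, F(8.5) = 6.8% and F(9.5) = 11.4%, so about half of the onsets fall after Year 8.5.

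**Step 2: crude percent over all eyes.** An onset first visible at visit v counts only if the subject still attends, with probability S(v) = (1 − a)^(v − 4):
crude = Σ S(v)·[F(v) − F(previous visit)]
At a = 8%, visits from Year 5 to Year 10 contribute 0.05 + 0.11 + 0.26 + 0.45 + 0.70 + 0.95 + 1.16 + 1.34 + 1.46 + 1.52 + 1.55, about 9.6%.

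**Step 3: other denominators.** With eyes that had an event or reached Year 10, the percent is crude / {crude + S(10)·[1 − F(10)]}. At a = 8% this is 9.56/(9.56 + 0.606 × 86.03) = 15.5%.

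| Attrition per year | Reach Year 10 | Crude, formula | Crude, simulated (1321 eyes) | Relative shortfall | Event-or-Year-10 denominator |
|---|---|---|---|---|---|
| 1.7% | 90% | 12.9% | 13.0% | 7% | 14.3% |
| 3% | 83% | 12.2% | 12.2% | 13% | 14.5% |
| 5% | 73% | 11.1% | 11.0% | 21% | 14.9% |
| 8% | 61% | 9.6% | 9.6% | 31% | 15.5% |

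Shortfall is (14.0 − simulated crude)/14.0. The standard error is about 1.0 point, so the gap is about 1 to 4.5 standard errors. A time-to-onset estimate returned 13.9% to 14.1% throughout. Attrition that loses 10% of subjects over the six years is 1 − 0.9^(1/6) = 1.74% a year.

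**Step 4: sensitivity to the assumptions.**

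- Slower loss (mean 1.2%, SD 1.0%): 5.9% becomes 5.4% to 3.9%.
- Chronic loss starting at surgery: F(10) = 1 − Φ{(30 − 18)/√(9 + 144)} = 16.6%, and crude is 15.4% to 11.6%, a shortfall of 7% to 30%.
- A simpler model: a Year 10 share of 10%, with 10% to 50% of eyes ending uniformly over Years 4 to 10. The shortfall is 3% to 15% under constant hazard and 5% to 25% if onset rises late.
- Reading noise of 2%, 3% or 4% (assumed SD on each reading and on baseline): the ever-crossed share with no dropout rises from 14.0% to about 15.0%, 16.5% and 18.6%. Crude at 1.7% attrition becomes 13.9%, 15.2% and 17.3%.
- Explantation just before the threshold in 30% of would-be events, with a Year 10 share of 10%: censoring at explant gives about 7.2%, a competing-event treatment gives about 10% × 0.7 = 7%, and counting the explant as an event gives 10.0% to 10.1%.

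**The case against.** The strongest reply is that the plan never says that lost eyes count as event-free and never calls the table a 10-year share. That is correct. A reader might infer that the SAP fixes an understatement; it does not. The all-eyes denominator is the likelier reading, not a stated one. Eyes with an event or a Year 10 reading would overstate (14.3% to 15.5% against 14.0%), and Year 10 completers alone would be about unbiased if loss is non-informative. This removes certainty about direction but strengthens the case for fixing the denominator in advance.

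A reader might also infer that most onsets are missed. They are not. At 1.7% attrition 13.0/14.0 = 93% are recorded, and at 8% 9.6/14.0 = 69%. Onsets recorded before an eye leaves still count.

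Noise matters too. First crossing over many readings is biased upward, so against the noise-free truth the net error of the crude percent has no settled sign, and at low attrition a plain time-to-onset estimate can lie further from it. That stands, and calls for a confirmed-crossing analysis.

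Explantation also limits any remedy. Protocol 9.3.7 links its consideration to density approaching about 1500 cells/mm², and SAP 3.1.1 drops later readings. A competing-event analysis alone does not recover onsets pre-empted in this way.

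Finally, the plan does some work already. By-visit tables show sample sizes, Protocol 9.1 admits late examinations to Year 10, and Protocol 9.5 and 9.7 ask for rescheduling and efforts to see subjects who move. Entry is staggered, so late entrants have less time to leave than assumed here. The SAP contents list has a redacted entry at page 11, before Adverse Events at page 15, which may hold a related analysis.

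**Conclusion.** The concern holds conditionally. The readable SAP leaves the denominator, horizon and at-risk counts of its marked-loss table unspecified. On the natural all-eyes reading, the percent falls with retention and understates what complete follow-up to Year 10 would show. The relative shortfall is about 7% to 31% for attrition of 1.7% to 8% a year. That rests on assumed loss rates, non-informative dropout after Year 4, no explantation and no measurement noise; the documents supply none of these figures.

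They do not support a flat statement that the table is biased downward: another denominator reverses the direction, and noise pushes crossings upward. The table is descriptive, no hypothesis is tested (Protocol 10.7), and the primary annualized loss rate is unaffected. The change should be made, because the table serves the secondary objective and the remedy is cheap.

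**What to change.** In SAP 4.1.2.2:

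- Keep the crude count, state its denominator, and show beside it the number of eyes with a Year 10 reading.
- Add the cumulative incidence of first onset by year since implantation (for example Years 5, 7 and 10). Follow each eye to its last evaluable on-lens reading and censor it there if the subject is lost or discontinued. Show eyes at risk at each year and subject-clustered confidence limits.
- In the main estimate treat explantation as a competing event (Aalen-Johansen). Add a sensitivity analysis that counts explantation for endothelial loss as an event.
- Add a sensitivity analysis that requires the crossing to be confirmed at the next reading. Label it as conservative: an onset first seen at the last visit cannot be confirmed, so in the noise-free example it returns F(9.5) = 11.4% rather than 14.0%.

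If the redacted pages already contain such an analysis, a cross-reference and the stated denominator suffice. The cost is a few lines of text and one or two tables from data already collected, with a slightly wider interval (standard error about 1.1 points against 0.9 to 1.0).
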